10.3.4. Reporting of SAEs and AESIs

SAE and AESI reporting

- All SAEs and AESIs will be recorded on the AE form of the eCRF. SAEs will also be recorded on the paper SAE report form
- The investigator or designated site staff will ensure all entered data are consistent
- An alert email for the SAE and AESI reports on the eCRF will automatically be sent by email to the sponsor or designee's safety mailbox via the EDC system

- The paper SAE report form will be faxed or emailed to the sponsor's designee (see the [Serious Adverse Event Reporting](#) details on page 2 of this protocol)

10.4. Appendix 4: Contraceptive and Barrier Guidance

10.4.1. Women of Childbearing Potential Definition

A female is considered a WOCBP unless she is either:

- a. **Postmenopausal:** A postmenopausal state is defined by continuous amenorrhea for at least 1 year without an alternative medical cause with an FSH measurement of > 40 IU/L. If a postmenopausal woman is using hormonal therapy, such as hormone replacement therapy or hormonal contraceptives, FSH levels might be suppressed and therefore an FSH test to confirm a postmenopausal state is not considered valid. In this case the postmenopausal state will need to be assessed by the investigator.
- b. **Surgically sterilized:** Women who have had a documented permanent sterilization procedure (eg, hysterectomy, bilateral salpingectomy, or bilateral oophorectomy)

10.4.2. Contraception Guidance

10.4.2.1. Female Contraception for Women of Childbearing Potential

WOCBP must use one of the following contraception methods from signing the ICF until the last dose of IMP.

The following Clinical Trials Facilitation and Coordination Group¹⁷ acceptable methods are permitted for efgartigimod studies:

- Progestogen-only oral hormonal contraception in which inhibition of ovulation is not the primary mode of action
- Male or female condom with or without spermicide
- Cap, diaphragm, or sponge with spermicide

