IMP infusion ^m	X ⁿ	X ^{o,p}																	
AE review	Continuous monitoring																		
Concomitant medications review	Continuous monitoring																		

	BL ^a	Study week																EDV ^b	SFV ^c
		1	2	3	4	5-7	8	9-11	12	13-15	16	17-23	24	25-35	36	37-47	48		
Study day (±2)	1	8	15	22	29	36-50	57	64-78	85	92-120	127	134-162	169	176-246	253	260-330	337		393

BL = baseline; clinESSDAI = clinical; ESSDAI; D = day; d/c = discontinuation; ECG = electrocardiogram; EDV = early discontinuation visit; ESSDAI = EULAR Sjögren’s syndrome disease activity index; ESSPRI = EULAR Sjögren’s Syndrome Patient-Reported Index; EULAR = European Alliance of Associations for Rheumatology; ICF = informed consent form; IgG = immunoglobulin G; IMP = investigational medicinal product; IV = intravenous; MFI = Multidimensional Fatigue Inventory; NA = not applicable; OSS = ocular staining score; PASS = patient acceptable symptom state; PCR = polymerase chain reaction; PD = pharmacodynamics; PGA = patient global assessment; PK = pharmacokinetics; RF = rheumatoid factor; SCR = screening; SFV = safety follow-up visit; SF-36 = 36-Item Short Form Survey; SGUS = salivary gland ultrasonography; SS-A = Sjögren’s syndrome-related antigen A; SS-B = Sjögren’s syndrome-related antigen B; SWSF = stimulated whole salivary flow; UWSF = unstimulated whole salivary flow; W = week.

^a BL will coincide with the final visit of a previous qualifying study. Grayed-out assessments may be conducted as part of the previous qualifying pSS studies.

^b The EDV will be performed within 7 days after last dose administration.

^c Participants will attend a safety follow-up visit 56 ± 3 days after the final IMP administration.

^d Weight mandatory at baseline.

^e Vital signs will be measured before collecting any blood sample or administering IMP infusions.

^f On IMP administration visits, blood samples must be collected predose (preferably within 2 hours before the infusion). On other visits, a blood sample may be collected at any time during the visit.

^h On IMP administration visits, blood samples for PK analyses will be collected predose (preferably within 2 hours before IMP administration). On other visits, a blood sample may be collected at any time during the visit.

ⁱ A PK sample will also be collected within 30 minutes after the end of IMP infusion.

^j The biological domain will remain blinded until the parent study is unblinded.

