5.1. Inclusion Criteria

Participants can be included in the study only if all of the following criteria apply:

1. Is at least the legal age of consent for clinical trials when signing the ICF
2. Is capable of providing signed informed consent, as described in Section 10.1.3, and complying with protocol requirements
3. Agrees to use contraceptive measures consistent with local regulations and the following:
 - a. WOCBP (defined in Section 10.4.1) must have a negative urine pregnancy test at baseline before receiving IMP (Section 10.4.2.1)
4. Has completed the qualifying efgartigimod pSS studies and agrees to continue study drug treatment without interruption in the extension study

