5.2. Exclusion Criteria

Participants will be excluded from the study if any of the following criteria apply:

1. Clinically significant disease (including newly diagnosed malignancy or cardiovascular disease) or intention to have surgery during the study; or any other medical condition that, in the investigator's opinion, would confound the results of the study or put the participant at undue risk
2. Pregnant or intention to become pregnant during the study
3. Any severe systemic pSS manifestation that may put the participant at undue risk based on the investigator's opinion

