6.9. Prior and Concomitant Therapy

Participants must maintain a stable regimen of medications throughout the study. Any medication (including over-the-counter or prescription medicines, recreational drugs, vitamins, and/or herbal supplements [including Chinese traditional medicine]) or other specific categories of interest that the participant is receiving at the time of enrollment or receives during the study must be recorded and include the following information:

- Reason for use
- Dates of administration, including start and end dates
- Dosage information (ie, dose and frequency)

The following medications or treatments are not permitted during the periods listed in [Table 4](#).

Table 4: Prior and Concomitant Therapy

Medication	Period participant is receiving IMP	Follow-up period
Live or live-attenuated vaccines	Prohibited	Permitted from 28 days after the last IMP dose
SCIg	Prohibited	Permitted
IVIg	Prohibited	Permitted
Corticosteroid steroids:		
Intra-muscular or intravenous corticosteroids	Prohibited	Permitted
Oral corticosteroids	Stable dose up to 10 mg daily	Permitted

Medication	Period participant is receiving IMP	Follow-up period
Inhaled corticosteroids	Permitted	Permitted
Intra-articular steroids	Prohibited	Permitted
Topical steroids	Topical (non-ophthalmic) steroids are permitted Topical ophthalmic steroids are prohibited.	Permitted
DMARDs		
Conventional DMARDs / Antimalarials	Permitted HCQ, CQ, AZA, MTX, MMF, leflunomide or cyclosporin at stable dose	Permitted
Cyclophosphamide	Prohibited	Permitted
Biologic DMARDs	Prohibited	Permitted
Targeted synthetic DMARDs:		
JAK inhibitors	Prohibited	Permitted
IMPs:		
IMP in another clinical trial	Prohibited	Permitted
Nonbiologic IMP in another clinical trial	Prohibited	Prohibited
Biologic IMP in another clinical trial	Prohibited	Prohibited
Other:		
Chinese traditional medicine with known immunomodulatory action	Prohibited	Permitted
Anticholinergic agents	Permitted at stable dose	Permitted
Topical symptomatic medications for pSS	At visits with planned efficacy assessments, participants will be required to withhold ophthalmic lubricants, ophthalmic lubricating ointments, hydroxyl cellulose ophthalmic inserts, and saliva substitutes before efficacy assessments are completed.	Permitted
Pharmacological topical ophthalmic agents (eg, NSAIDs, cyclosporine)	Prohibited	Permitted

Medication	Period participant is receiving IMP	Follow-up period

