7.1. Discontinuation of IMP

7.1.1. Permanent Discontinuation

Permanent discontinuation of IMP occurs when the participant stops receiving the IMP before the end of the study, does not resume receiving IMP, and does not withdraw informed consent.

The investigator will document the primary reason for early discontinuation of IMP.

Participants who permanently discontinue IMP will complete the EDV.

The study sites will attempt to perform the EDV within 7 days after the participant's final IMP administration. The SFV will occur 56 ± 3 days after the participant's final IMP administration.

Additionally, the following circumstances will result in the permanent discontinuation of IMP:

- The participant becomes pregnant or intends to become pregnant (see Section 8.3.5)
- The investigator considers discontinuing IMP is in the participant's best interest (the sponsor will be informed)
- The participant develops an SAE or AE that contraindicates further administration of IMP in the investigator's opinion or an AE of CTCAE severity grade 4 that is considered related to IMP by the sponsor
- The participant develops a new or recurrent malignancy except for basal cell carcinoma of the skin, regardless of relationship to IMP
- The participant receives a prohibited medication or substance (Section 6.9)

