8.3.5. Pregnancy Testing

- WOCBP will be tested for pregnancy. Urine tests for pregnancy will occur at the time points specified in the SoA (Section 1.3)
- Pregnancy testing in WOCBP will be conducted at the end of relevant systemic exposure (ie, at the SFV)
- Additional pregnancy testing could be performed, as deemed necessary by the investigator or required by local regulations, to establish the absence of pregnancy at any time during the study

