Copyright © 2009, 2010, 2012, 2016, 2018, 2019, 2021, 2024 IQVIA. All rights reserved. The contents of this document are confidential and proprietary to IQVIA Holdings Inc. and its subsidiaries. Unauthorized use, disclosure or reproduction is strictly prohibited.

For Urinalysis, we do not have week 2, week 4, week 8, week 12 visit, as in that case the following window:

[figure not shown]
Table B: Non-efficacy Analysis Visit Definition for Urinalysis.

Phase	Target Day	Assigned Study Day (Inclusive)		Week Assigned
		From	To	
Treatment	Not applicable ^a			Baseline
	113	2	141	Week 16
	169	142	211	Week 24
	253	212	295	Week 36
	337	296	Up to the date of SFV.	Week 48
Safety Follow-up	NA	NA	NA	SFV

For Urine pregnancy testing, we only have Baseline, and Safety Follow-up schedules the following window:

Table B: Non-efficacy Analysis Visit Definition for Urine Pregnancy testing.

Phase	Target Day	Assigned Study Day (Inclusive)	Week Assigned
-------	------------	--------------------------------	---------------

Copyright © 2009, 2010, 2012, 2016, 2018, 2019, 2021, 2024 IQVIA. All rights reserved. The contents of this document are confidential and proprietary to IQVIA Holdings Inc. and its subsidiaries. Unauthorized use, disclosure or reproduction is strictly prohibited.

		From	To	
Treatment	Not applicable ^a			Baseline
Safety Follow-up	NA	NA	NA	SFV

^a Last available non-missing measurement from the parent study ARGX-113-2106.

[figure not shown]
For efficacy assessments (e.g., ClinESSDAI), wider window will be considered as follows:

Table C: Efficacy Analysis Visit Definition for ClinESSDAI.

Target Day	Assigned Study Day (Inclusive)		Week Assigned
	From	To	
Not applicable ^a			Baseline
113	2	141	Week 16
169	142	197	Week 24
225	198	239	Week 32
253	240	267	Week 36
281	268	295	Week 40
309	296	323	Week 44
337	324	Until study discontinuation	Week 48

^a Last available non-missing measurement from the parent study ARGX-113-2106.

Note: ClinESSDAI will only be conducted at weeks 32, 36, 40, and 44 if the participant is a non-responder at week 24 and not considered a therapeutic failure by the PI.

Copyright © 2009, 2010, 2012, 2016, 2018, 2019, 2021, 2024 IQVIA. All rights reserved. The contents of this document are confidential and proprietary to IQVIA Holdings Inc. and its subsidiaries. Unauthorized use, disclosure or reproduction is strictly prohibited.

a Last available non-missing measurement from the parent study ARGX-113-2106.

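### Required contraception ends at the last dose, 53 to 59 days before the point the protocol itself calls the end of relevant systemic exposure

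*Protocol*

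**What the plan says.** Protocol section 10.4.2.1 fixes the contraception period for women of childbearing potential (WOCBP): "WOCBP must use one of the following contraception methods from signing the ICF until the last dose of IMP". It gives no reason for ending there.

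Section 8.3.5, which schedules the final pregnancy test, reads: "Pregnancy testing in WOCBP will be conducted at the end of relevant systemic exposure (ie, at the SFV"). Footnote c of the Schedule of Activities dates that visit: "Participants will attend a safety follow-up visit 56 ± 3 days after the final IMP administration". Section 7.1.1 repeats the same interval for participants who stop early.

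Four other provisions bear on the point:

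- Inclusion criterion 3 (section 5.1): "Agrees to use contraceptive measures consistent with local regulations and the following". No duration is attached.
- Exclusion criterion 2 (section 5.2): "Pregnant or intention to become pregnant during the study".
- Section 7.1.1 lists, among the reasons for permanently stopping drug, "The participant becomes pregnant or intends to become pregnant (see Section 8.3.5").
- The Schedule of Activities places urine pregnancy tests at baseline, at the early discontinuation visit (EDV) and at the SFV. SAP section 6.3 windows only the first and last of these: "For Urine pregnancy testing, we only have Baseline, and Safety Follow-up schedules the following window".

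**The concern.** The two sections cannot both be right as written. If relevant exposure lasts until the SFV, ending contraception at the last infusion leaves an exposed interval with no protocol requirement. If exposure ends sooner, section 8.3.5 misplaces its end.

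The stake is participant safety. Followed literally, the protocol lets a participant stop contraception on the day of her last infusion. The rest of the plan does not treat that day as the end of drug-related caution. Live vaccines are "Permitted from 28 days after the last IMP dose" (section 6.9, Table 4), and SAP section 17.1.1 counts adverse events as treatment-emergent for 60 days after dosing. Neither window is a contraception standard, but both show that a tail of zero days is out of line with the rest of the plan.

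**Working it through.** This is date arithmetic plus a reading of the related provisions.

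**Inputs**

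| Item | Value | Source |
|---|---|---|
| End of required contraception | last dose (day 0 here) | Protocol 10.4.2.1 |
| End of relevant systemic exposure | SFV | Protocol 8.3.5 |
| Timing of SFV | 56 ± 3 days after last dose | Protocol 1.3 footnote c; 7.1.1 |
| Planned last dose | week 47 (QW), week 46 (Q2W) | Protocol 1.2; 1.3 footnote o |
| SFV column in the schedule | day 393 | Protocol 1.3 |

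**Uncovered interval.** Gap = SFV day − day on which contraception may stop.

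- Shortest: 56 − 3 − 0 = 53 days; 53/7 = 7.6 weeks
- Nominal: 56 − 0 = 56 days; 56/7 = 8.0 weeks
- Longest: 56 + 3 − 0 = 59 days; 59/7 = 8.4 weeks

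**Cross-check on the study calendar.** Day of last dose = 7 × week + 1.

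- QW: 7 × 47 + 1 = day 330. The 56 ± 3 rule puts the SFV on days 383 to 389; the schedule's day 393 is 393 − 330 = 63 days after the last dose.
- Q2W: 7 × 46 + 1 = day 323. The rule gives days 376 to 382; day 393 is 393 − 323 = 70 days after the last dose.

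Day 393 is 56 days after the week 48 visit (day 337), at which no dose is planned. The explicit 56 ± 3 rule gives the shorter gap and is the one used here, so 53 to 59 days is not inflated.

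**Does another provision close the gap?**

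- *Local regulations (5.1).* They may require longer use at some sites, but the protocol sets no minimum, so cover could differ by site.
- *Entry exclusion (5.2).* Section 4.4 makes the SFV part of completing the study, so a pregnancy already planned for follow-up is screened out at entry. Unplanned pregnancy and a later change of mind are not.
- *Stopping drug for intended pregnancy (7.1.1).* The dose already given becomes the last dose, and under 10.4.2.1 the contraception duty ends with it. The participants most likely to conceive are released at once.
- *Testing.* A test detects a pregnancy; it does not prevent one. A participant who completes treatment has no scheduled test between baseline and the SFV. The EDV test, for early discontinuers, falls within 7 days of the last dose, near the start of the interval.
- *Response to a pregnancy (8.4.5).* Stopping drug has no effect once the last dose has been given.

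None of these sets a contraception duration after the last dose.

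**The case against.** The strongest reply is that the exposure claim rests on a parenthesis in a bullet about when to test. The SFV is the only scheduled visit after week 48 for a completer, so a post-exposure test would fall there even if exposure had ended weeks earlier. On that reading the mismatch could equally be resolved by rewording section 8.3.5. Choosing between the two needs pharmacokinetic and embryo-fetal data, which the protocol leaves to the Investigator's Brochure. Ending at the last dose may also be deliberate: the list of methods is framed as applying to efgartigimod studies generally, and section 10.4.2.2 asks nothing of men. Table 4 lifts most other drug restrictions in follow-up, so the vaccine row alone overstates the caution applied there. Finally, the change would ask contraception of a woman who has stopped treatment in order to conceive.

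Part of this stands. The interval is an upper bound, no fetal hazard is shown, and the vaccine and adverse-event windows only give scale. But section 8.3.5 does equate the two time points, and nothing visible explains why contraception should end earlier. If the sponsor has data for a shorter period, the text still needs correcting: that period should be stated in 10.4.2.1 and 8.3.5 changed to match. Without such data, the precautionary direction is the one the visible text supports, and it applies equally to a participant who stops in order to conceive, because her exposure does not end sooner.

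**Conclusion.** The concern holds. By its own wording the protocol leaves 53 to 59 days after the last dose with no contraception requirement beyond whatever local regulations impose. The figure assumes that relevant exposure lasts until the SFV, as section 8.3.5 says; the true interval may be shorter. Up to approximately 30 participants are planned, and the number who are WOCBP is not given. No endpoint, estimate or conclusion changes. This should be corrected as a participant-safety inconsistency. Confidence is medium, because the exposure data that would settle the exact duration are not in the documents.

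**What to change.** In section 10.4.2.1, replace the end point of the contraception requirement with the SFV, 56 ± 3 days after the last dose. State that this also covers participants who discontinue early, including those who stop under section 7.1.1 because they intend to become pregnant. The uncovered interval then falls from 53–59 days to 0. Align the participant information if it differs; it was not available for this review.

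The cost is one sentence in a protocol amendment and about 8 additional weeks of contraception for each WOCBP, with no new visits, tests or analyses. Section 2 already foresees an amendment to add qualifying studies, so the change could be made then.

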10.4.2.2. Male Contraception

There are no contraception requirements for men in this study.

10.5. Appendix 5: Operational Considerations for COVID-19 Risk Mitigation

Participants will be tested for SARS-CoV-2 if they are symptomatic or if applicable law requires testing.

During the study, the sites will implement all recommendations issued by the local government regarding the spread of COVID-19, including specific guidelines related to clinical research performed in clinical research centers.

This appendix is intended for use only if unforeseen changes in the COVID-19 pandemic result in new restrictions at the site or new risks for participants or site staff from attending visits at the site.

Testing for COVID-19 is not required during the study unless required by local authorities. However, it is recommended that participants who develop COVID-19 symptoms while receiving IMP be tested, with results reported for the study.

Critical Parameters to Be Collected During the Study

All assessments will be performed as indicated in the SoA (Section 1.3). If assessments cannot be performed due to the COVID-19 pandemic, the following information must be collected from the first visit through end-of-study: all AE and concomitant medication reporting, IMP administration, questionnaires, and protocol-required laboratory assessments.

10.6. Appendix 6: Home Study Visits

A home nurse can travel to the participant's home to conduct visits (or meet the participant at a convenient alternate location). For each home visit, the investigator or designee will confer with the participant via an audio or video interview to elicit AEs and concomitant medications and the participant's general well-being. The investigator or designee will also ensure the participant has completed all required efficacy assessments that can be done at home (eg, questionnaires). Any scheduled assessments will be conducted before the home nurse administers IMP.

10.7. Appendix 7: Efficacy Endpoint Data

10.7.1. ESSDAI

Table 7: ESSDAI: Domain and Item Definitions and Weights

Domain [Weight]	Activity level	Description
Constitutional [3] Exclusion of fever of infectious origin and voluntary weight loss	No = 0	Absence of the following symptoms
	Low = 1	Mild or intermittent fever (37.5 to 38.5°C)/night sweats and/or involuntary weight loss of 5 to 10% of body weight
	Moderate = 2	Severe fever (> 38.5°C)/night sweats and/or involuntary weight loss of > 10% of body weight
Lymphadenopathy [4] Exclusion of infection	No = 0	Absence of the following features
	Low = 1	Lymphadenopathy \geq 1 cm in any nodal region or \geq 2 cm in inguinal region
	Moderate = 2	Lymphadenopathy \geq 2 cm in any nodal region or \geq 3 cm in inguinal region, and/or splenomegaly (clinically palpable or assessed by imaging)
	High = 3	Current malignant B-cell proliferative disorder
Glandular [2] Exclusion of stone or infection	No = 0	Absence of glandular swelling
	Low = 1	Small glandular swelling with enlarged parotid (\leq 3 cm), or limited submandibular or lachrymal swelling
	Moderate = 2	Major glandular swelling with enlarged parotid (> 3 cm), or important submandibular or lachrymal swelling
Articular [2] Exclusion of osteoarthritis	No = 0	Absence of currently active articular involvement
	Low = 1	Arthralgias in hands, wrists, ankles, and feet, accompanied by morning stiffness (> 30 minutes)
	Moderate = 2	1 to 5 (of 28 total count) synovitis
	High = 3	\geq 6 (of 28 total count) synovitis
Cutaneous [3] Rate as “No activity” stable long-lasting features related to damage	No = 0	Absence of currently active cutaneous involvement
	Low = 1	Erythema multiforme
	Moderate = 2	Limited cutaneous vasculitis, including urticarial vasculitis, or purpura limited to feet and ankle, or subacute cutaneous lupus
	High = 3	Diffuse cutaneous vasculitis, including urticarial vasculitis, or diffuse purpura, or ulcers related to vasculitis

Table 7: ESSDAI: Domain and Item Definitions and Weights (Continued)

Domain [Weight]	Activity level	Description
Pulmonary [5] Rate as “No activity” stable long-lasting features related to damage, or respiratory involvement not related to the disease (tobacco use etc)	No = 0	Absence of currently active pulmonary involvement
	Low = 1	Persistent cough or bronchial involvement with no radiographic abnormalities on radiography; or radiological or HRCT evidence of interstitial lung disease with: no breathlessness and normal lung function test
	Moderate = 2	Moderately active pulmonary involvement, such as interstitial lung disease shown by HRCT with shortness of breath on exercise (NHYA II) or abnormal lung function tests restricted to: 70% > DLCO ≥ 40% or 80% > FVC ≥ 60%
	High = 3	Highly active pulmonary involvement, such as interstitial lung disease shown by HRCT with shortness of breath at rest (NHYA III, IV) or with abnormal lung function tests: 70% > DLCO ≥ 40% or 80% > FVC ≥ 60%
Renal [5] Rate as “No activity” stable long-lasting features related to damage, and renal involvement not related to the disease. If biopsy has been performed, please rate activity based on histological features first	No = 0	Absence of currently active renal involvement with proteinuria < 0.5 g/day, no hematuria, no leucocyturia, no acidosis, or long-lasting stable proteinuria due to damage
	Low = 1	Evidence of mild active renal involvement, limited to tubular acidosis without renal failure or glomerular involvement with proteinuria (between 0.5 and 1 g/day) and without hematuria or renal failure (GFR ≥ 60 mL/min)
	Moderate = 2	Moderately active renal involvement, such as tubular acidosis with renal failure (GFR < 60 mL/min) or glomerular involvement with proteinuria between 1 and 1.5 g/day and without hematuria or renal failure (GFR ≥ 60 mL/min) or histological evidence of extra-membranous glomerulonephritis or important interstitial lymphoid infiltrate
	High = 3	Highly active renal involvement, such as glomerular involvement with proteinuria > 1.5 g/day or hematuria or renal failure (GFR < 60 mL/min), or histological evidence of proliferative glomerulonephritis or cryoglobulinemia related renal involvement
Muscular [6] Exclusion of weakness due to corticosteroids	No = 0	Absence of currently active muscular involvement
	Low = 1	Mild active myositis shown by abnormal EMG or biopsy with no weakness and creatine kinase (N < CK ≤ 2N)

Table 7: ESSDAI: Domain and Item Definitions and Weights (Continued)

Domain [Weight]	Activity level	Description
	Moderate = 2	Moderately active myositis proven by abnormal EMG or biopsy with weakness (maximal deficit of 4/5), or elevated creatine kinase ($2N < CK \leq 4N$)
	High = 3	Highly active myositis shown by abnormal EMG or biopsy with weakness (deficit $\leq 3/5$) or elevated creatine kinase ($> 4N$)
PNS [5] Rate as “No activity” stable long-lasting features related to damage or PNS involvement not related to the disease	No = 0	Absence of currently active PNS involvement
	Low = 1	Mild active peripheral nervous system involvement, such as pure sensory axonal polyneuropathy shown by NCS or trigeminal (V) neuralgia
	Moderate = 2	Moderately active PNS involvement shown by NCS, such as axonal sensory-motor neuropathy with maximal motor deficit of 4/5, pure sensory neuropathy with presence of cryoglobulinemic vasculitis, ganglionopathy with symptoms restricted to mild/moderate ataxia, CIDP with mild functional impairment (maximal motor deficit of 4/5 or mild ataxia), or cranial nerve involvement of peripheral origin (except trigeminal [V] neuralgia)
	High = 3	Highly active PNS involvement shown by NCS, such as axonal sensory-motor neuropathy with motor deficit $\leq 3/5$, peripheral nerve involvement due to vasculitis (mononeuritis multiplex, etc), severe ataxia due to ganglionopathy, CIDP with severe functional impairment: motor deficit $\leq 3/5$ or severe ataxia
CNS [5] Rate as “No activity” stable long-lasting features related to damage or CNS involvement not related to the disease	No = 0	Absence of currently active CNS involvement
	Low = 1	Moderately active CNS features, such as cranial nerve involvement of central origin, optic neuritis, or multiple sclerosis–like syndrome with symptoms restricted to pure sensory impairment or proven cognitive impairment
	High = 3	Highly active CNS features, such as cerebral vasculitis with cerebrovascular accident or transient ischemic attack, seizures, transverse myelitis, lymphocytic meningitis, multiple sclerosis–like syndrome with motor deficit

Table 7: ESSDAI: Domain and Item Definitions and Weights (Continued)

Domain [Weight]	Activity level	Description
Hematological [2] For anemia, neutropenia, and thrombopenia, only autoimmune cytopenia must be considered Exclusion of vitamin or iron deficiency, drug-induced cytopenia	No = 0	Absence of autoimmune cytopenia
	Low = 1	Cytopenia of autoimmune origin with neutropenia ($1000 < \text{neutrophils} < 1500/\text{mm}^3$), and/or anemia ($10 < \text{hemoglobin} < 12 \text{ g/dL}$), and/or thrombocytopenia ($100\,000 < \text{platelets} < 150\,000/\text{mm}^3$); or lymphopenia ($500 < \text{lymphocytes} < 1000/\text{mm}^3$)
	Moderate = 2	Cytopenia of autoimmune origin with neutropenia ($500 \leq \text{neutrophils} \leq 1000/\text{mm}^3$), and/or anemia ($8 \leq \text{hemoglobin} \leq 10 \text{ g/dL}$), and/or thrombocytopenia ($50\,000 \leq \text{platelets} \leq 100\,000/\text{mm}^3$); or lymphopenia ($\leq 500/\text{mm}^3$)
	High = 3	Cytopenia of autoimmune origin with neutropenia ($\text{neutrophils} < 500/\text{mm}^3$) and/or anemia ($\text{hemoglobin} < 8 \text{ g/dL}$) and/or thrombocytopenia ($\text{platelets} < 50\,000/\text{mm}^3$)
Biological [1]	No = 0	Absence of any of the following biological features
	Low = 1	Clonal component and/or hypocomplementemia (low C4 or C3 or CH50) and/or hypergammaglobulinemia or high IgG level between 16 and 20 g/L
	Moderate = 2	Presence of cryoglobulinemia and/or hypergammaglobulinemia or high IgG level $> 20 \text{ g/L}$, and/or recent onset hypogammaglobulinemia or recent decrease of IgG level ($< 5 \text{ g/L}$)

Source: Seror et al, 2011⁸

C3 = Complement component 3; C4 = Complement component 4; CH50 = Total hemolytic complement; CIDP = chronic inflammatory demyelinating polyneuropathy; CK = creatine kinase; CNS = central nervous system; DLCO = diffusing capacity of the lungs for carbon monoxide; EMG = electromyogram; ESSDAI = EULAR Sjögren's syndrome disease activity index; FVC = forced vital capacity; GFR = glomerular filtration rate; HRCT = high-resolution computed tomography; IgG = immunoglobulin G; N = normal; NCS = nerve conduction studies; NHYA = New York Heart Association (classification); PNS = peripheral nervous system

